# Statistical analysis plan: The Reach

## Programme

Evaluating institution: Sheffield Hallam University Principal investigator(s): [name], [name] and [name]

Project title 	The Reach Programme	
Developer (Institution)	VRU for Leicester, Leicestershire and Rutland, Leicester City Council, Leicestershire County Council	
Evaluator (Institution)	Sheffield Hallam University	
Principal investigator(s)	[name], [name], [name]	
SAP author(s)	[name], [name]	
Trial design	Blocked Randomised Controlled Trial (RCT) design. Within each block (i.e. school), referred young people (YP) will be randomised to receive the Reach programme or BAU contro (i.e. two arms).	
Trial type	Efficacy with internal pilot	
Evaluation setting	School	
Target group	Children and YP aged 11 to 16 years old who are at risk of suspension or who are persistently absent from school, and where there are concerns about future involvement in anti- social behaviour and crime as both a victim or perpetrator.	
Number of participants	12 schools, 600 YP	

Primary outcome and data source	Externalising score (Teacher report SDQ)		
Secondary outcome and data source	
 
Internalising score (Teacher report SDQ)
 
Externalising score (Self report SDQ)
 
Internalising score (Self report SDQ)
 
Prosocial behaviour score (Teacher report SDQ)
 
Prosocial behaviour score (Self report SDQ)
 
Variety of delinquency score (SRDS)
 
Volume of delinquency score (SRDS)
 
Number of suspensions (source: Leicester City Council and Leicestershire County Council)
 
School attendance (source: Leicester City Council and Leicestershire County Council)
 
Offending data (source: VRU Leicester)
 
		

# SAP version history

Version	Date	Changes made and reason for revision
1.0	09/05/24	NA

### Introduction

The Reach Programme is targeted intervention aimed at YP (young people) aged 11-16 in secondary schools (years 7-11) who are at risk of suspension (i.e. they have carried out behaviour in their school that would normally qualify for a suspension) or who are persistently absent from school, have 3 indicators of vulnerability (e.g. looked after, domestic violence or substance misuse in the home) and where there are concerns about future involvement in anti-social behaviour and crime as both a victim or perpetrator. YP are referred to the Reach Programme directly from schools. A team of 10 Youth Workers working across the 12 schools deliver one to one sessions to YP over a period of 6 months, covering a set of core components as follows:

- Relationship Building
- Understanding behaviour
- Social Skills training
- Confidence, Wellbeing and Resilience
- Positive Family, Peer, and Community Relationships
- Identifying and Achieving Aspirations
- Recreational Activity

The Reach evaluation is designed as an efficacy trial with internal pilot. The internal pilot phase of the evaluation is now complete, and the efficacy phase began in January 2024 across the same 12 schools that were recruited for the pilot phase. Whist the sample of 12 schools remains the same, the YP recruited to the efficacy phase are different to those recruited at the pilot phase. Please see the Reach Protocol for a more detailed description of the intervention and associated documents (referral form, Theory of Change and Logic Model).

# **Design overview**

#### Table 1: Design overview

Trial design, including number of arms		Two-arm randomised control trial		
Unit of randomisation		Individual participant		
Stratification variables (if applicable)		School (to balance allocation within schools)		
Primon	variable	Behavioural difficulties		
outcome	measure (instrument, scale, source)	Teacher report SDQ externalising score [0 to 20]		
Secondary outcome(s)	variable(s)	
 
Emotional regulation and peer relationships (Teacher report SDQ)
 
Behavioural difficulties (Self report SDQ)
 
Emotional regulation and peer relationships (Self report SDQ)
 
Prosocial behaviour (Teacher report SDQ)
 
Prosocial behaviour (Self report SDQ)
 
Variety of delinquency
 
Volume of delinquency
 
Number of suspensions
 
Attendance at school (%)
 
Level of offending
 
		
	measure(s) (instrument, scale, source)	
 
Teacher report SDQ internalising score [0 to 20]
 
Self report SDQ externalising score [0 to 20]
 
Self report SDQ internalising score [0 to 20]
 
Teacher report prosocial score [0 to 10]
 
Self report prosocial score [0 to 10]
 
Variety of delinquency (SRDS)
 
Volume of delinquency (SRDS)
 
Number of suspensions
 
Attendance at school (%)
 
Level of offending
 
		

Baseline for	variable	Behavioural difficulties	
primary outcome	measure (instrument, scale, source)	Teacher report SDQ externalising score [0 to 20]	
Baseline for secondary		
 
Emotional regulation and peer relationships (Teacher report SDQ)
 
Behavioural difficulties (Self report SDQ)
 
Emotional regulation and peer relationships (Self report SDQ)
 
Prosocial behaviour (Teacher report SDQ)
 
Prosocial behaviour (Self report SDQ)
 
Variety of delinquency
 
Volume of delinquency
 
Number of suspensions
 
Attendance at school (%)
 
Level of offending
 
	
outcome	measure (instrument, scale, source)	
 
Teacher report SDQ internalising score [0 to 20]
 
Self report SDQ externalising score [0 to 20]
 
Self report SDQ internalising score [0 to 20]
 
Teacher report prosocial score [0 to 10]
 
Self report prosocial score [0 to 10]
 
Variety of delinquency (SRDS)
 
Volume of delinquency (SRDS)
 
Number of suspensions
 
Attendance at school (%)
 
Level of offending
 
	

### Sample size calculations overview

The power calculations assume an ITT analyses with 100% complete baseline/outcome data and that the only systematic difference between the Reach group and the control group is their group membership (all other difference are random). Table 2 below presents the sample size calculations, showing firstly the estimates presented in the protocol from which the sample size for the study was drawn (600 YP) to achieve an MDES of 0.18 - 0.19. This was determined a priori using correlation estimates (0.50 to 0.60), drawn from the EEF Adventure Learning Trial (Willis et al., 2023), and drawing on the Reach baseline pilot data for the ICC (0.13). The sample size of 600 YP was discussed with the delivery partner and the timescales to achieve this sample size were agreed, also taking into account practical considerations in terms of delivery. Subsequent to this the internal pilot phase has now been completed, giving an updated participant level correlation of 0.32 (calculated from the full set of pilot data), which would achieve an MDES of 0.21 for the same sample size (Table 2).

Sample = 600 CYP across 24 clusters (25 CYP per cluster)		Protocol	Randomisation: drawing on Reach pilot data for ICC and correlation estimates*
Minimum Detectable Effect Size (MDES)		0.18-0.19 sds	0.21 sds
Pre-test/	level 1 (participant)	0.50 to 0.60	0.32 (R  =0.10)
post-test correlations	level 2 (cluster)	n/a 	n/a 
Intracluster correlations (ICCs)	level 1 (participant)	n/a²	n/a²
	level 2 (cluster)	0.13	0.13
Alpha 		0.05	0.05
Power		0.80	0.80
One-sided or two-sided?		Two	Тwo

Table 2: Sample size calculations

\*Internal pilot phase was completed subsequent to protocol submission and is drawn on to inform the SAP

The power calculations were undertaken using a formula and checked using the PowerUp software (Dong et al., 2013, sheet BIRA1\_1r). For the Reach evaluation, this is a blocked RCT

<sup>2 Dong, N., & Maynard, R. A. (2013). PowerUp!: A tool for calculating minimum detectable effect sizes and minimum required sample sizes for experimental and quasi-experimental design studies. Journal of Research on Educational Effectiveness, 6(1), 24-67.doi: 10.1080/19345747.2012.673143. https://www.causalevaluation.org/power-analysis.html

design such that in each 'block' (school), YP are randomly allocated to Reach programme, or to the control group. The power analysis was conducted in the following way:

$$MDES_{RCT(Blocked)} \sim M_{J-L-1} \sqrt{\frac{ICC_2(1-R_2^2)\varphi}{J} + \frac{(1-ICC_2)(1-R_1^2)}{P(1-P)Jn}}$$

Where:

- J=number of blocks (schools )
- n=number of individuals per block (YP per school)
- L= number of (block level) covariates to be used in the impact analyses (this might include a variable used to stratify or minimise in randomisation)
- P = the proportion of individuals assigned to the intervention in each location/block which would be 0.5 within a balanced design.
- $M_{J-L-1}$  is the group effect multiplier ... value from the t-distribution for 2-tailed test with alpha=0.05 & beta=0.80, equal variances assumed with J-L-1 degrees of freedom.
- *ICC*2 is the cluster (location/block) level ICC; the proportion of variance in the outcome between blocks.
- $R_2^2$  = proportion of between cluster/block level variance that is reduced by covariate(s) block level explanatory power.
- $R_1^2$  = proportion of within-block variance that is reduced by covariate(s) participant level explanatory power.
- $\varphi$  = Treatment effect heterogeneity (which is usually set to be zero for efficacy trials larger effectiveness trials might be powered to detect this).

If we assume zero treatment effect heterogeneity and a balanced design ... P=0.5 and  $\varphi$  = 0, equation 1.1 simplifies to equation 1.2:

$$MDES_{RCT(Blocked)} \sim 2M_{J-L-1} \sqrt{\frac{(1-ICC_2)(1-R_1^2)}{Jn}}$$

This removes  $R_2^2$  from the equation (because  $\varphi = 0$ ) and so only explanatory power at the YP level influences the statistical sensitivity of the blocked-RCT design.

The impact of the ICC on sensitivity is the opposite of what is seen with clustered RCT design that randomise at the cluster level. For clustered designs with randomisation at the cluster level (e.g. school), higher ICCs are associated with higher MDES estimates. For blocked-RCT

designs with randomisation at the individual level in each 'block' (e.g. school), higher ICCs are associated with lower MDES estimates. This is because the blocked-RCT design fixes things so that the cluster (or block) level is completely accounted for – i.e. the Reach intervention and BAU control groups are randomised in exactly the same locations (or blocks). Therefore, as the cluster-level variance in the outcome increases proportionally (i.e. as ICCs increase), an increasing quantity of random 'noise' is completely accounted for and this results in increased statistical sensitivity (as seen with decreasing MDES estimates).

As ICC2 increases, (1-ICC2) and (therefore) the MDES estimate decreases. So, to estimate the smallest effect size that a blocked design could detect as statistically significant (P,0.05, two-tailed) with a statistical power of 0.80 or higher [MDES], the following details are needed:

- J=number of schools = 12 at pilot; 12 at stage 2 ~ 24 in all. n= CYP per school = 25. L= number of (block level) covariates =0
- *M**J*-*L*-1 is the group effect multiplier ... value from the t-distribution for 2-tailed test with alpha=0.05 & beta=0.80, equal variances assumed with J-L-1 (24-0-1=23) degrees of freedom.
- *ICC*2 is the cluster (location/block) level ICC; the proportion of variance in the outcome between blocks: Unknown, estimated as 0.13 from baseline pilot data.
- $R_1^2$  = proportion of within-block variance that is reduced by covariate(s) participant level explanatory power. This was estimated at between 0.50 and 0.60 based on findings from Adventure Learning (Willis et al. 2023). Also presented in table 2 are calculations based on a participant level correlation of 0.32 calculated from the full set of pilot data for this trial that is now available.

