#### Table 3: Example analysis model RQ1

Analysis and Sample	Level 1 (pupil) Covariates	Level 2 (school) Covariates	Outcome Variable
Empty model			
ITT sample (RQ1)	Group (1=Reach participants school, O=Control group participants) Baseline teacher report SDQ externalising score (centred around the mean)	Mean school-level baseline teacher report SDQ externalising score (centred around school level Grand mean)	Follow up teacher report SDQ externalising score

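### The MDES is computed for 24 schools and no school-level covariate, but the SAP describes 12 schools and a primary model with one such covariate

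*SAP*

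**What the plan says.** The section 'Sample size calculations overview' defines "J=number of blocks (schools") and L as the count of block-level covariates in the impact analyses. It then fills these in as "J=number of schools = 12 at pilot; 12 at stage 2 ~ 24 in all", "n= CYP per school = 25" and "L= number of (block level) covariates =0", which gives 24 − 0 − 1 = 23 degrees of freedom. Table 2 repeats 24 clusters of 25. It prints an MDES of 0.18–0.19 in the protocol column (correlations 0.50 to 0.60) and 0.21 with the pilot correlation of 0.32.

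Other parts of the SAP describe a different structure:

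- The summary table at the front gives "12 schools, 600 YP".
- The Introduction says that "the efficacy phase began in January 2024 across the same 12 schools that were recruited for the pilot phase", and that "the YP recruited to the efficacy phase are different to those recruited at the pilot phase".
- The Analysis section pools the two phases for the headline analysis, in a two-level model with random intercepts for schools. No term for phase, or for school by phase, is listed.
- Table 3 lists, at school level, "Mean school-level baseline teacher report SDQ externalising score (centred around school level Grand mean").

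**The concern.** The figure of 24 is reached by counting each of the 12 schools once per phase. The pupils differ between phases, so the total of 600 is sound, but the number of schools and the number per school are not those of the trial described. Setting L to zero also conflicts with the SAP's definition of L, because the primary model has one school-level covariate.

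Both inputs enter through the multiplier M, whose degrees of freedom are J − L − 1. Too many degrees of freedom make M, and so the MDES, too small under that rule. Table 2 is the SAP's statement of what the headline analysis can detect at 80% power, and a null result will be read against it. The number of schools behind it should be the number in the trial.

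**Working it through.** **Formula.** This is the SAP's simplified equation, with zero treatment-effect heterogeneity and equal allocation:

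MDES = 2 × M × √[(1 − ICC)(1 − R₁²) / (J × n)], where M = t(0.975, df) + t(0.80, df) and df = J − L − 1.

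**Inputs from the sample size section and Table 2.** ICC 0.13; two-sided alpha 0.05; power 0.80; complete data; correlation r of 0.32 (pilot) or 0.50 to 0.60 (protocol). I take R₁² = r². The section's input list labels 0.50–0.60 as R₁² itself, but Table 2 labels the values as correlations, and the printed results are reproduced only on that reading.

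**The part that does not change.** J × n is 24 × 25 = 12 × 50 = 600 either way, so only M moves.

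- r = 0.32: 2 × √(0.87 × 0.8976 / 600) = 0.07215
- r = 0.50: 2 × √(0.87 × 0.75 / 600) = 0.06595
- r = 0.60: 2 × √(0.87 × 0.64 / 600) = 0.06093

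**Results.** The first row reproduces the SAP's own figures.

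| Basis | df | M | r = 0.32 | r = 0.50 | r = 0.60 |
|---|---|---|---|---|---|
| As printed: J = 24, L = 0 | 23 | 2.926 | 0.211 | 0.193 | 0.178 |
| Only L changed: J = 24, L = 1 | 22 | 2.932 | 0.212 | 0.193 | 0.179 |
| Only J changed: J = 12, L = 0 | 11 | 3.077 | 0.222 | 0.203 | 0.187 |
| Both changed: J = 12, L = 1 | 10 | 3.107 | 0.224 | 0.205 | 0.189 |
| Pupil-level df: 600 − 12 − 2 | 586 | 2.806 | 0.203 | 0.185 | 0.171 |

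The 586 removes one degree of freedom for each of the 12 schools and two for the treatment and baseline coefficients.

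**Split of the change at r = 0.32.** Correcting J moves the MDES from 0.2111 to 0.2220 (+0.011). Correcting L as well takes it to 0.2242 (+0.002). The total is 0.013, and 3.107 / 2.926 = 1.062, an increase of about 6%.

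**Power at an effect of 0.21, r = 0.32 (non-central t).** 0.796 with 23 df, 0.755 with 11 df, 0.747 with 10 df and 0.828 with 586 df.

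**The case against.** The strongest reply is that J − L − 1 is the wrong rule for this analysis in any case. Those degrees of freedom belong to a treatment effect that varies between schools. The SAP sets heterogeneity to zero, randomises within schools, plans random intercepts with no random treatment slope, and limits itself to conditional inference. The treatment contrast is then estimated within schools on roughly pupil-level degrees of freedom, and the MDES is about 0.20 whether J is 12 or 24. On that basis the printed 0.21 is slightly conservative. This stands. It is why the power of 0.75 cannot be quoted without its condition, and why 0.22 should not simply replace 0.21. It does not rescue the text, because the SAP states the J − L − 1 rule and fills it with a school count that it contradicts elsewhere. The printed 0.21 lies between the two defensible values and belongs to neither.

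A second reply is that the 24 may mean school-by-phase blocks, since each phase recruits different young people. That is possible, but the SAP calls the units schools, names school as the only stratifier in Table 1, and has no phase term in the model. If blocks were meant, the SAP has to say so.

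Two smaller points also stand. L on its own is negligible. And the protocol column reports what the protocol gave, so overwriting it would falsify a record.

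A reader might infer that the sum itself is wrong or that pupils were counted twice. Neither is so: the printed values follow from the printed inputs, and the 600 are distinct pupils.

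**Conclusion.** Wrong as written, with minor consequences. The inputs J = 24, n = 25 and L = 0 contradict the SAP's summary table, Introduction, Analysis section and Table 3, which together give J = 12, n of about 50 and L = 1. For the pilot correlation the MDES is 0.22 under the plan's own rule with 10 df, and 0.20 with pupil-level df. For the protocol correlations it is 0.19–0.20 and 0.17–0.19 respectively.

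A reader might conclude that the trial is underpowered. The document does not support that. Power of about 0.75 at 0.21 holds only if school-level degrees of freedom apply; under the zero heterogeneity and random-intercept model that the SAP states, power at 0.21 is about 0.83. All of these figures keep the SAP's assumptions of an ICC of 0.13, equal allocation, 600 young people and no missing data. No estimate, test or decision rule in the plan changes.

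**What to change.** 1. In the input list of the sample size section and in Table 2, state 12 schools with about 50 young people each, and L = 1.
2. For the pilot correlation, restate the MDES as 0.22 under the J − L − 1 rule (10 df), noting power of about 0.75 at 0.21. Beside it give 0.20 with pupil-level df (about 586). Say which basis applies to the planned analysis and why.
3. Leave the protocol column as the historical record. Add the recomputed values in a footnote or a new column: 0.19–0.20 with 10 df and 0.17–0.19 with pupil-level df.
4. If 24 school-by-phase blocks were intended, say so instead, justify the degrees of freedom, and put those blocks in the analysis model.

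The cost of items 1 to 3 is SAP wording and one recalculation, with no change to recruitment or to the sample size. Item 4, if taken, would also amend the model specification.

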#### Primary outcome analysis

The primary outcome measure for the Reach trial is behavioural difficulties as measured by the externalising score contained within the teacher version of the SDQ (Goodman, 2001). The SDQ, teacher version is a 25-item scale used to assess behaviour in the school context in 4–16-year-olds. This consists of 5 subscales; conduct problems, hyperactivity scale, emotional problems scale, peer problems scale and prosocial scale. The externalising score measures "behavioural difficulties" and is the sum of the conduct and hyperactivity scales. This links well with the Theory of Change in terms of improved behaviour management, reduction in negative behaviours in school and reduction in problem behaviours both in and out of school. This is also one of YEF's core outcome measures. The primary research question for the Reach trial is set out below:

**RQ1** What is the difference in behavioural difficulties measured using the externalising score from the teacher report Strengths and Difficulties Questionnaire (SDQ) between the intervention group, when compared to a 'business as usual' control?

Table 3 below provides an example analysis model for RQ1.

#### Table 3: Example analysis model RQ1

Analysis and Sample	Level 1 (pupil) Covariates	Level 2 (school) Covariates	Outcome Variable
Empty model			
ITT sample (RQ1)	Group (1=Reach participants school, O=Control group participants) Baseline teacher report SDQ externalising score (centred around the mean)	Mean school-level baseline teacher report SDQ externalising score (centred around school level Grand mean)	Follow up teacher report SDQ externalising score

#### Secondary outcome analysis

The variables to be employed for the secondary outcome analysis derive from the teacher report SDQ, the self-report SDQ, the self report delinquency scale (SRDS) and administrative data on suspensions, attendance and offending data as described below and presented in table 1. The teacher report SDQ internalising score is the sum of the emotional and peer problems scales and will form one of the secondary outcomes which links to improved emotional regulation and increased self-esteem and emotional well-being, and also increased network of positive peers. The teacher report prosocial score forms a further secondary outcome and links to improved social skills. The self-report SDQ (completed by the YP) externalising score, internalising score and prosocial score will be used as secondary outcomes, linking to the LM in the same way as the teacher version, and providing validation of findings from the primary outcome.

The self-report delinquency scale (SRDS) will also be used as a secondary outcome. This measures delinquent behaviour by assessing the frequency and severity of any delinquent acts committed. This fits with the LM in terms of reduction of negative behaviours at school and reduction in suspensions or problem behaviours, and improved attendance at school.

A further three outcome measures will be analysed from administrative data; suspensions, attendance and offending behaviours. Using this administrative data provides further validation to the self report measures in terms of attendance and offending behaviours which link to the LM as described above. Using data on suspensions as a secondary outcome links directly to the LM in terms of reduction in suspensions.

Attendance data is reported as a percentage of attendance at school by the YP. This was collected at the point of referral from the school, and collected again from the schools at the

same time as the teacher report SDQ outcome measure. This data will be verified with the councils, who will then share the data with SHU. Data on suspensions (number of previous suspensions) was also collected from schools at the point of referral. This data is being collected directly from the local councils by the delivery partner at the point of closure to the Reach Programme, and the equivalent time period for the control group and shared with SHU to be matched into the final dataset using YP name/school/date of birth to achieve accurate matching. The secondary outcome analysis research questions are set out below:

- **RQ2** What is the difference in emotional regulation and peer relationships measured using the internalising score of the teacher report SDQ between the intervention group, when compared to a 'business as usual' control?
- **RQ3** What is the difference in behavioural difficulties measured using the externalising score from the self report Strengths and Difficulties Questionnaire (SDQ) between the intervention group, when compared to a 'business as usual' control?
- **RQ4** What is the difference in emotional regulation and peer relationships measured using the internalising score of the self report SDQ between the intervention group, when compared to a 'business as usual' control?
- **RQ5** What is the difference in prosocial behaviour measured using the prosocial score of the teacher report SDQ between the intervention group, when compared to a 'business as usual' control?
- **RQ6** What is the difference in prosocial behaviour measured using the prosocial score of the self report SDQ between the intervention group, when compared to a 'business as usual' control?
- **RQ7** What is the difference in offending behaviours measured using "variety of delinquency score" from the self-report delinquency scale (SRDS) between the intervention group, when compared to a 'business as usual' control?
- **RQ8** What is the difference in offending behaviours measured using "volume of delinquency score" from the self-report delinquency scale (SRDS) between the intervention group, when compared to a 'business as usual' control?
- **RQ9** What is the difference in attendance at school measured using administrative data between the intervention group, when compared to a 'business as usual' control?
- **RQ10** What is the difference in number of suspensions measured using administrative data between the intervention group, when compared to a 'business as usual' control?
- **RQ11** What is the difference in offending behaviours measured using administrative data between the intervention group, when compared to a 'business as usual' control?

Analysis of secondary outcomes will be conducted in the same way as for the primary outcome, table 4 below provides an example analysis model for RQ7.

